7.4.9 Week 4 (Dose 12)

Pre-dose:

1. Complete physical examination (including body weight)
2. Vital signs
3. Oximetry
4. Concomitant medications review
5. AE review
6. Obtain blood and urine samples for PK prior to dosing
7. Administer any routine pulmonary medications and airway clearance techniques, including SABA and/or LABA, Pulmozyme, inhaled corticosteroids and/or antibiotics
8. Spirometry (FEV₁, FVC, and FEF₂₅₋₇₅)
9. Administer study drug

Post-dose:

1. Symptom-directed physical examination within 2 hours post dose
2. Vital signs within 2 hours post dose
3. Oximetry within 2 hours post dose
4. Spirometry at 20, and 60 minutes, 4 hours post dose
5. Obtain the following samples for PK:
 - Blood at 1, 2, 3, 4, and 8 hours post dose
6. Obtain sample for sweat chloride determination

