**Table 7: Time point for Spirometry MAD**

Time point	Target Date/Time	Interval for Analysis
Baseline	Day 1 dose start time	Most recent value prior to first dose
Day 1 10 min Post-dose	Day 1 dose end time+10 min	]Day 1 dose end time, Day 1 dose end time +20min]
Day 1 30 min Post-dose	Day 1 dose end time+30 min	]Day 1 dose end time+20min, Day 1 dose end time +45min]
Day 1 60 min Post-dose	Day 1 dose end time+60 min	]Day 1 dose end time+45min, Day 1 dose end time +90min]
Day 1 2 hr Post-dose	Day 1 dose end time+2 hours	]Day 1 dose end time+90min, Day 1 dose end time +3h]
Day 1 4 hr Post-dose	Day 1 dose end time+4 hours	]Day 1 dose end time+3h, Day 1 dose end time +6h]
Day 1 8 hr Post-dose	Day 1 dose end time+8 hours	]Day 1 Dose end time+6h, Day 2[
Day 3 Pre-dose	Day 3 dose start time	[Day 2, Day 3 dose start time[
Day 3 20 min Post-dose	Day 3 dose end time +20 min	]Day 3 dose end time, Day 3 dose end time +40min]
Day 3 60 min Post-dose	Day 3 dose end time +60 min	]Day 3 dose end time+40min, Day 3 dose end time +2h]
Day 3 4 hr Post-dose	Day 3 dose end time+4 hours	]Day 3 dose end time+2h, Day 4[
Day 4	Day 4	]Day 3, Day 5[
Day 5 Pre-dose	Day 5 dose start time	[Day 5, Day 5 dose start time[
Day 5 20 min Post-dose	Day 5 dose end time +20 min	]Day 5 dose end time, Day 5 dose end time +40min]
Day 5 60 min Post-dose	Day 5 dose end time +60 min	]Day 5 dose end time+40min, Day 6]
Day 8 Pre-dose	Day 8 dose end time	[Day 7, Day 8 dose end time[
Day 8 20 min Post-dose	Day 8 dose end time +20 min	]Day 8 dose end time, Day 8 dose end time +40min]
Day 8 60 min Post-dose	Day 8 dose end time +60 min	]Day 8 dose end time+40min, Day 10]
Day 15 Pre-dose	Day 15 dose start time	]Day 10, Day 15 dose start time[
Day 15 20 min Post-dose	Day 15 dose end time +20 min	]Day 15 dose end time, Day 15 dose end time +40min]
Day 15 60 min Post-dose	Day 15 dose end time +60 min	]Day 15 dose end time+40min, Day 17]
Day 22 Pre-dose	Day 22 dose start time	]Day 17, Day 22 dose start time[
Day 22 20 min Post-dose	Day 22 dose end time +20 min	]Day 22 dose end time, Day 22 dose end time +40min]
Day 22 60 min Post-dose	Day 22 dose end time +60 min	]Day 22 dose end time+40min, Day 24 ]
Day 26 Pre-dose	Day 26 dose start time	]Day 24, Day 26 dose start time[
Day 26 20 min Post-dose	Day 26 dose end time +20 min	]Day 26 dose end time, Day 26 dose end time +40min]
Day 26 60 min Post-dose	Day 26 dose end time +60 min	]Day 26 dose end time+40min, Day 26 +3 days ]

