#### 4.2.7.4. Sweat Chloride

**Table 17: Time points for Sweat Chloride MAD**

Time point	Target	Interval for Analysis
Baseline	Day 1 dose start time	Most recent value prior to first dose
Day 26	Day 26	[Day 1 dose end time, Day 26+3 days]
Day 33	Day 33	[Day 26+4 days ; Day 33+ 7 days]
Day 54	Day 54	[Day 33+8 days ; End of Study]

If several assessments are done on the same day, the average of these assessments will be used.

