#### 4.8.2. MAD

##### 4.8.2.1. ppFEV1 (%)

The ppFEV1 value, absolute change from baseline and % change from baseline (relative change) will be presented descriptively over time (considering all time points from the visit windows for this parameter), per treatment group.

Graphical representation may be provided (mean change+ 95% CI overtime). Particularly a zoom on the data for the first 24 hours following first dose will be given).

In addition, the SAD and MAD ppFEV1 for the first 24 hours will be pooled in order to provide more robust data to the first day evolution.

The mixed-model analysis will be performed with repeated time measures on the change from baseline ppFEV1 as outcome variable and including treatment, baseline ppFEV1 value, time and interaction between time and treatment as covariates. By default, an unstructured covariance matrix will be used, unless convergence issue, in which case other covariance matrix will be explored. Adjusted means and corresponding confidence interval will be presented.

For visits with a dose, several spirometry assessments (pre and post dose) are planned. Subjects usually suffer from fatigue due to the multiple assessments, resulting in low post-dose values of FEV1. Thus the following time points, concentrating on the pre-dose evaluations during treatment, and the post-treatment time points will be considered: Baseline, Day 3 pre-dose, Day 4, Day 5 pre-dose, Day 8 pre-dose, Day 15 pre-dose, Day 22 pre-dose, Day 26 pre-dose, Day 26 4 hours post-dose, Day 33 and Day 54. Differences versus Placebo will be estimated at Day 26 pre-dose, Day 26 4 hours post-dose, Day 33 and Day 54.

A sensitivity analysis including presence/absence of *Pseudomonas aeruginosa* at Baseline as a covariate will be performed.

Analyses to explore the dose response using the MCPMOD methodology as described in the SAD section will be followed. The change from baseline in ppFEV1 at Day 26 pre-dose, Day 26 4 hours post-dose and Day 33 will be assessed.

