## 3. ANALYSES

### 3.1. ppFEV1 (%)

Descriptive summaries will be performed on Per Protocol Populations and Sensitivity Population excluding outliers of PPFEV1. Summaries will be repeated on subgroups of PPFEV1 at baseline for the 3 populations.

The mixed-model analysis described in the SAP will be repeated on the Per Protocol and Sensitivity Populations (using the following time points: Baseline, Day 4, Day 5 pre-dose, Day 8 pre-dose, Day 15 pre-dose, Day 22 pre-dose, Day 26 pre-dose, Day 26 4 hours post-dose, Day 33 and Day 54. Differences versus Placebo will be estimated at Day 15, Day 26 pre-dose, Day 26 4 hours post-dose, Day 33 and Day 54). Differences versus Placebo at Day 15 will also be assessed on Exploratory Population (in addition to planned time points).

The mixed model analysis will also be carried out on subgroups of PPFEV1 at baseline for the 3 populations. Due to the small sample size, the following time points only will be included in the model: Day 15 pre-dose, Day 26 pre-dose and Day 33.

The sensitivity analysis including presence/absence of *Pseudomonas aeruginosa* at Baseline as a covariate will be repeated on Per Protocol Populations. Day 15 will be added as time point of interest for both Exploratory and Per Protocol Populations.

Analyses to explore the dose response using the MCPMOD methodology as described in the SAP will be followed and repeated on Per Protocol Populations. The change from baseline in ppFEV1 at Day 15 pre-dose (also on Exploratory Population), Day 26 pre-dose, Day 26 4 hours post-dose, Day 33 and Day 54 will be assessed.

In addition to the dose-responses shapes described in the SAP, a quadratic model with umbrella-shape will be tested. Parameters of the dose-responses shapes models may be adapted to fit the data.

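### SAP Table 7 has no window for the Day 26 4-hour ppFEV1 reading, which is a planned MAD contrast and MCPMod time point, and places that reading under Day 26 60 min

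*SAP*

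**What the plan says.** SAP 4.8.2.1 (MAD ppFEV1) lists the Day 26 4-hour reading among the mixed-model time points and then uses it twice. For the placebo comparisons: "Differences versus Placebo will be estimated at Day 26 pre-dose, Day 26 4 hours post-dose, Day 33 and Day 54". For MCPMod, the change from baseline "at Day 26 pre-dose, Day 26 4 hours post-dose and Day 33 will be assessed". The descriptive summary of the same variable is tied to the window table: "considering all time points from the visit windows for this parameter".

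Protocol 7.4.9 schedules the reading at Dose 12: "Spirometry at 20, and 60 minutes, 4 hours post dose".

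SAP Table 7 gives Day 26 three rows: pre-dose, 20 min and 60 min. The 60 min interval is "Day 26 dose end time+40min, Day 26 +3 days", open at the lower end and closed at the upper. The next row is Day 33, which opens at Day 26 plus 4 days. Day 3, by contrast, has its own 4-hour row: "Day 3 dose end time+2h, Day 4".

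Section 3.1 of the post hoc SAP uses the time point again ("Differences versus Placebo will be estimated at Day 15, Day 26 pre-dose, Day 26 4 hours post-dose, Day 33 and Day 54") and adds no window.

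**The concern.** An analysis time point that is named for testing should have a stated derivation, and this one has none. Table 7 sends the 4-hour reading to a row labelled 60 min, where it sits beside the true 60-minute reading.

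The SAP gives no spirometry rule for two readings in one window. It does have local rules elsewhere. For sweat chloride, "If several assessments are done on the same day, the average of these assessments will be used". For glucose (SAP 4.8.2.8), the model takes the first value of the day. Both are narrower than a general rule for several readings in a window, but they show that the question was considered for other variables and not for spirometry.

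The choice is not neutral on the SAP's own reasoning, because section 4.8.2.1 expects fatigue from repeated spirometry to lower post-dose FEV1. Two programmers working from the same text could produce different Day 26 values, and one of them could find no data for the 4-hour contrast.

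**Working it through.** No sample size, power or alpha figure is involved. The check assigns scheduled readings to windows and counts what is affected.

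**Inputs.** Scheduled Day 26 post-dose spirometry at 20, 60 and 240 minutes (protocol 7.4.9). Intervals from SAP Table 7. Post-dose times count from the end of inhalation (note to SAP Table 5). Four active doses plus placebo. 32 planned MAD subjects (SAP 4.1).

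**Step 1: assignment under Table 7 as written, with Day 3 as comparator.**

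| Minutes after end of dosing | Day 26 row | Day 3 row |
|---|---|---|
| 20 | 20 min (0 < 20 ≤ 40) | 20 min (0 < 20 ≤ 40) |
| 60 | 60 min (60 > 40) | 60 min (40 < 60 ≤ 120) |
| 240 | 60 min (240 > 40, limit Day 29) | 4 hr (240 > 120, before Day 4) |

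The upper limit on Day 26 is Day 26 + 3 = Day 29, and the Day 33 row opens at Day 26 + 4 = Day 30. No interval yields Day 26 4 hours. With complete data, the Day 26 60 min window holds 32 × 2 = 64 readings where 32 are intended.

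**Step 2: what uses the missing time point.**
- Main SAP contrasts: 4 doses × 4 times = 16 estimates, of which 4 × 1 = 4 are affected. MCPMod: 1 of 3 time points.
- Post hoc SAP, whole-population models: 4 doses × 5 times = 20 estimates in each population, of which 4 are affected. MCPMod: 1 of 5 time points. The post hoc models by baseline ppFEV1 subgroup use only Day 15, Day 26 pre-dose and Day 33, so they do not use it.

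**Step 3: assignment with the Day 3 cut applied to Day 26.** 60 min falls in the interval above 40 and up to 120 minutes. 240 min falls in the interval above 120 minutes and before Day 27. Each row then holds one scheduled reading per subject. This assumes that dosing ends before 20:00, so that 4 hours later is still Day 26.

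**Step 4: what lies on Days 27 to 29.** After Dose 12 the protocol schedules only PK sampling before the Day 33 visit (7.4.10 and 7.4.11). Readings on Days 27 to 29 in subjects given Dose 12 would therefore be unscheduled spirometry.

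**Step 5: two neighbouring items.**
- The main SAP's model list includes Day 3 pre-dose, but protocol 7.4.4 schedules only post-dose spirometry that day. No contrast or MCPMod analysis is planned at that time point, and the post hoc SAP leaves it out.
- The Day 5 60 min window runs to Day 6, so it also takes the conditional 4-hour reading of protocol 7.4.6. No contrast or MCPMod analysis uses that row.

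**The case against.** The best defence is that the label Day 26 4 hours post-dose matches exactly one scheduled reading, whose actual time is recorded under protocol 7.1, so a competent programmer would simply select it. The SAD model is expressly run on the time windows, while the MAD model paragraph does not say so. Much of this stands. A reader might infer that the contrast cannot be estimated or that data are missing. The documents do not support that: the reading is collected and recoverable, and the time point is empty only if Table 7 is applied literally. What remains is that the SAP states no other route, and that the 60 min descriptive row, which is tied to the windows, is ambiguous however the model is programmed.

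A reader might also infer that End of Treatment visits of early discontinuers will fall in this window at a predictable day. Protocol 7.4.12 ties the 7-day visit to Dose 12 and gives no day for that visit after early discontinuation, so no such count can be made. Nor is the SAP silent on missed doses in general: section 4.2.7.1 and Table 5 set the target date when a dose is missed.

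**Conclusion.** The point holds as a minor defect. Table 7 assigns a named analysis reading to the wrong label and leaves the named time point without a derivation. It reaches 4 of 16 planned dose-versus-placebo estimates and 1 of 3 MCPMod analyses for MAD ppFEV1, with the post hoc SAP carrying the same gap. The endpoint is exploratory, and protocol 4.1.3 says that the study is not powered for efficacy. The primary safety objective and the SAD ppFEV1 analysis do not use this time point.

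It is tempting to add that the other three contrast time points are untouched. Their readings are windowed correctly, but their estimates come from one joint model with a common baseline term and an unstructured covariance, so dropping or redefining one time level could shift them slightly. The documents give no basis for sizing that shift.

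The counts assume that all four MAD doses are studied. The 64 readings also assume 32 subjects with complete Day 26 spirometry.

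**What to change.** In SAP Table 7, for subjects given Dose 12:
- End Day 26 60 min at 2 hours after the end of dosing (above 40 minutes, up to and including 2 hours).
- Add Day 26 4 hr, above 2 hours after the end of dosing and before Day 27, as on Day 3.
- State that readings from Day 27 to Day 26 plus 3 days carry no Day 26 post-dose label, but stay in the listings and in the at-least-once count of FEV1 falls of 15% or more (SAP 4.10.1.4). This sentence is needed because Day 3 is followed directly by a Day 4 row, while Day 26 has no row until Day 30. Keeping the present upper limit would avoid the gap, but would let a reading taken days later count as a 4-hour value.

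Add one rule for spirometry: where several readings fall in a window, use the one closest to target for by-time-point summaries and models. Closest-to-target is a suggestion; any single stated rule removes the ambiguity. Apply it to the Day 5 60 min window too.

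Delete Day 3 pre-dose from the main SAP's model list. Refer to the amended table from the post hoc SAP. If results have already been produced, record which derivation was used for Day 26 4 hours.

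The cost is SAP wording and programming. No new data are needed.

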##### 4.8.2.2. FEV1 (L)

FEV1 value, change from baseline and % change from baseline will be presented descriptively over time, per treatment group.

##### 4.8.2.3. FVC (L)

FVC value, change from baseline and % change from baseline will be presented descriptively over time, per treatment group.

##### 4.8.2.4. FEF25/75 (L)

FEF25/75 value, change from baseline and % change from baseline will be presented descriptively over time, per treatment group.

##### 4.8.2.5. Sweat Chloride (mmol/L)

Sweat chloride value and change from baseline will be presented descriptively over time, per treatment group. Graphical representation may be provided (mean change+ 95% CI overtime).

If several assessments are done on the same day, the average of these assessments will be used. See Section 4.2.1 for definition of baseline.

#### 4.8.2.6. C-Reactive Protein (CRP) (mg/L)

CRP value and change from baseline will be presented descriptively over time, per treatment group.

Graphical representation will be provided (mean change from baseline +95% CI overtime).

#### 4.8.2.7. Erythrocyte Sedimentation Rate (ESR) (mg/L)

ESR value and change from baseline will be presented descriptively over time, per treatment group.

Graphical representation will be provided (mean change from baseline+95% CI overtime).

#### 4.8.2.8. Glucose

Glucose value and change from baseline will be presented descriptively over time, per treatment group.

A mixed model with repeated time measures on the change from baseline of glucose (mmol/L) as outcome variable and including treatment, baseline glucose value, time and interaction between time and treatment as covariates. By default, an unstructured covariance matrix will be used, unless convergence issue, in which case other covariance matrix will be explored. Adjusted means and corresponding confidence interval will be presented.

For some visits with a dose, several glucose assessments pre and/or post-dose are planned. We expect glucose values to differ post dose through the same day as meals are consumed; for stability of the data only the first glucose assessment performed at the selected visit days will be used.

Thus the following time points will be included in the repeated measures analysis: Baseline (baseline, Day 7 pre-dose, Day 15 pre-dose, Day 22 pre-dose, Day 33 and Day 54. Differences versus placebo will be estimated at Day 22, Day 33 and Day 54.

A sensitivity analysis including presence/absence of Cystic Fibrosis Related Diabetes with or without glucose intolerance at Baseline as a covariate will be performed.

Cystic Fibrosis related Diabetes at Baseline is defined as medical history term containing 'diabetes' 'cystic fibrosis related diabetes', 'diabetes mellitus'. Glucose tolerance will be defined as medical history term containing 'glucose tolerance impaired'. Descriptive statistics will be provided as appropriate.

The MCPMOD methodology will be applied to evaluate the dose-response, with change from baseline of glucose at Day 22 pre-dose as dependent variable. Thresholds of -0.5, -1, -2 will be tested as sizes of interest of treatment effect.

Graphical representation will be provided (mean change +95% CI overtime).

#### 4.8.2.9. CFQ-R (Cystic Fibrosis Questionnaire – Revised)

The CFQ-R subject health-related quality of life questionnaire will be administered using the self-administered format (Adolescent and Adult version in the protocol Appendix 3), according

to the study schedule for MAD cohorts only. The CFQ-R is administered prior to any other test or procedure on each of the required study days (Baseline, Day 15, Day 33 and Day 54).

#### Cystic Fibrosis Questionnaire- Revised Respiratory Symptoms Score (CFQ-R RSS)

The CFQ-R RSS is calculated based on mean score of Questions 40 to 46 excluding question 43 as below if  $\leq 3$  item scores are missing:

Assuming a coding of 1 to 4 with categories such as

1=A great deal / Always

2=Somewhat / Often

3=A little / Sometimes

4=Not at all / Never,

$$\text{CFQ-R RSS} = \text{mean} [(\text{resp40}, \text{resp41}, \text{resp42}, \text{resp44}, \text{resp45}, \text{resp46})-1]/3*100;$$

The score will be missing if more than three of the six scores are missing.

Descriptive summary overtime will be provided for the values and change from baseline at each time point following the time windows, by treatment group.

A mixed model analysis with repeated time measures on the change from baseline of CFQ-R RSS as outcome variable, including treatment, baseline CFQ-R RSS value, time and interaction between time and treatment as covariates will be performed. By default, an unstructured covariance matrix will be used, unless convergence issue occurs, in which case other covariance matrix will be explored. Adjusted means and corresponding confidence interval will be presented. The following time points will be included in the repeated measures analysis: Baseline, Day 15, Day 33 and Day 54. Differences versus placebo will be estimated at Day 33 and Day 54.

A dose-response analysis using MCPMOD methodology will be performed with change from baseline of CFQ-R RSS at Day 33 as dependent variable, the treatment (0, 6.25, 12.5, 25, 50 mg) and CFQ-R RSS at baseline as factors. Thresholds of +4, +5, +8 and +10 will be tested as sizes of interest of treatment effect.

#### CFQ-R Other Domains:

Descriptive summary over time will be provided for the values and change from baseline at each time point following the time windows, by treatment group.

Details for re-coding are provided in [http://www.psy.miami.edu/cfq\\_QLab/scoring.html](http://www.psy.miami.edu/cfq_QLab/scoring.html) .

All CFQ-R domain scores will be reported in listings.

#### 4.8.2.10. Weight (kg)

Weight value and change from baseline will be presented descriptively over time at each time point (Baseline, Day 4, Day 15, Day 22, Day 26, Day 33, Day 54) per treatment group.

A mixed model with repeated time measures on the change from baseline of Weight as outcome variable, including treatment, baseline weight value, time and interaction between time and treatment as covariates will be performed. By default, an unstructured covariance matrix will be

used, unless convergence issue, in which case other covariance matrix will be explored. Adjusted means and corresponding confidence interval will be presented. The following time points will be included in the repeated measures analysis: Baseline, Day 15, Day 33 and Day 54. Differences versus placebo will be estimated at Day 33 and Day 54.

A dose-response analysis using MCPMOD methodology will be performed with change from baseline of weight at Day 33 as dependent variable, the treatment (0, 6.25, 12.5, 25, 50 mg) and weight at baseline as factors. Thresholds of 0.5, 1, 2 and 3 (kg) will be tested as sizes of interest of treatment effect.

#### **4.9. Pharmacokinetic Evaluations**

In the SAD portion of the study, sample collections for support of PK analysis are planned as follows:

- Blood (i.e. serum): pre-dose (time 0), 0.5, 1, 2, 3, 4, 12, 24, 48, 54, 72, 168 hours post-dose.
- Urine: Pre-dose (time 0); Pooled from 0 to 4, 4 to 12, and 12 to 24 hours post-dose; and 48, 72, and 168 hours post dose.
- Sputum: 3 samples obtained within first 6 hours post dose; 24 hours post dose; Day 4 (72 hours post dose); and Day 8 (168 hours post dose)

In the MAD portion of the study, sample collections for support of PK analysis are planned as follows:

Week 1, Dose 1

- Serum: 0, 0.5, 1, 2, 3, 4, 12; pre-Dose 2 (48 hours post-dose 1)
- Urine: Pre-dose; Pooled from 0 to 4 and 4 to 12 hours post Dose 1.
- Sputum: pre-dose, 3 samples obtained within first 6 hours post Dose 1.

Week 4, Dose 12

- Serum: pre-dose (0), 1, 2, 3, 4, 8, 24, 96, 144 (7 days post-last dose) and 648 hours (28 days post-last dose).
- Urine: Pre-dose; 24 and 96 hours, post-dose.

Additional sample collections are planned on interim study days during the MAD portion of the study. The measured concentrations will be presented in listings and used to confirm adequate QR-010 exposure; however, they will not be used to support generation of PK parameters. Additionally, urine concentrations that did not come from pooled collections or for which sample volumes were not collected will only be displayed in listings and will not be used to support generation of renal PK parameters.

The planned PK parameters for each portion of the study may be found in Table 26 below. Area under the serum concentration curve (AUC) will be generated using the linear-log trapezoidal rule.

